**For all hypothesis:**

$\mu_1$  is average of measurements with comparator at 2 weeks;

$\mu_2$  is the average of measurements at 2 week follow up (investigational device);

$\mu_3$  is the average of measurements at 8 – 12 week follow up (investigational device);

and  $|M_{NI}|$  is the margin of non – inferiority

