**Table 4 Endpoints, test methods and hypotheses**

	Hypothesis	Test Method	Endpoint	Acceptance Criteria
A	Subjects reduced exertion performing 6MWT compared to previous prosthesis (primary outcome)	BORG scale	Mean difference in BORG score pre and post 6MWT compared to comparator	$H_0: \mu_1 \leq \mu_2$ $H_1: \mu_1 > \mu_2$ $p<0.05$
B	Subjects improved performance in 6MWT compared to previous prosthesis.	6MWT (meters)	Average distance walked in 6MWT compared to comparator	$H_0: \mu_1 \geq \mu_2$ $H_1: \mu_1 < \mu_2$ $p<0.05$
C	Subjects report on average no worse support in sit to stand and stand to sit than with previous prosthesis.	Self-report: PMQ (Questions 9 and 10) Likert scale 0-4	Total score of PMQ questions 9 and 10 compared to comparator	$H_0: \mu_1 \geq \mu_2 +  M_{NI} $ $H_1: \mu_1 < \mu_2 +  M_{NI} $ $ M_{NI}  = 1$ $p<0.05$
D	Subjects perceived safety in hill descent is no worse than with previous prosthesis.	Self-report: Modified PEQ 14F (rate your safety when walking down a steep hill using the prosthesis) Likert Scale 1-10	Average score compared to comparator	$H_0: \mu_1 \geq \mu_2 +  M_{NI} $ $H_1: \mu_1 < \mu_2 +  M_{NI} $ $ M_{NI}  = 1$ $p<0.05$
E	Subjects perceived safety in stair descent is no worse than with previous prosthesis.	Self-report: Modified PEQ 13D (rate your safety when walking downstairs using the prosthesis) Likert Scale 1-10	Average score compared to comparator	$H_0: \mu_1 \geq \mu_2 +  M_{NI} $ $H_1: \mu_1 < \mu_2 +  M_{NI} $ $ M_{NI}  = 1$ $p<0.05$
F	Subjects perceive no speed limitation while walking with the investigational device.	Self-report(yes/no): „Are you satisfied with your walking speed using your prosthesis/test prosthesis?”  Support question: “Do you feel that your walking speed is limited by your prosthesis/test prosthesis?”	Proportion of subjects (p) reporting satisfaction with walking speed on investigational device.	$H_0: p < 80\%$ $H_1: p \geq 80\%$ $p<0.05$

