L	The investigational device provides ease of use of gait functions no worse than previous device	Self-report: PMQ (Questions 1 and 3-6) Likert scale 0-4  Objective measure L-test	Total score of PMQ questions 1, 3-6.  Proportion of subjects (p) successfully completing the L-test using gait functions.	For PMQ score: $H_0: \mu_1 \geq \mu_2 +  M_{NI} $ $H_1: \mu_1 < \mu_2 +  M_{NI} $ $ M_{NI}  = 2,5$ $p < 0.05$  For L-test: $H_0: p < 80\%$ $H_1: p \geq 80\%$ $p < 0.05$
M	Side effects N/A	Side effects	Occurrence of side effects	N/A

N	Mobility using the investigational device is no worse than with the comparator	PMQ total score (0-48)	Average total score of the PMQ	$H_0: \mu_1 \geq \mu_2 +  M_{NI} $ $H_1: \mu_1 < \mu_2 +  M_{NI} $ $ M_{NI}  = 5,5$ $p < 0.05$
O	Activity level increases with longer adaptation period on the investigational device	Activity reports from the knee (daily steps, use time)	Activity level after 8-12w follow up compared to 2w follow up on investigational device	$H_0: \mu_2 \geq \mu_3$ $H_1: \mu_2 < \mu_3$ $p < 0.05$

Informative endpoint: In house usability questionnaire (Perceived weight, size, look, ergonomics, fit w/clothes, battery life, preference, falls questionnaire)

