## 10 Statistical Considerations

### 10.1 Statistical design and procedures

Outcomes at each timepoint will be visually inspected for normality using histograms and qq-plots. If the data are deemed to be normal the hypotheses will be tested using a two-tailed, paired, student's t-test. Non-normal data will be tested using the Wilcoxon signed-rank test.

Acceptance criteria for the data, as applicable, is defined in Table 4 **Endpoints, test methods and hypotheses**. Subgroup analysis will not be performed as no subgroups are defined.

Repeated measures analysis has the advantage of increased power vis-à-vis group allocations and reduction in error variance associated with individual difference, as each subject acts as its own control. This is important for studying amputees as the group is a small proportion of the total population, and with specific inclusion/exclusion criteria the total eligible population becomes very small, making it difficult to find and recruit subjects to attain an acceptable level of power. This limited population pool often results in slightly heterogeneous sample, as the amputees available are few and far between, in every sense. Furthermore, no single amputation procedure and therefore amputated stump is exactly the same, making the experience of each amputee a bit unique. The within-subject design significantly reduces the individual differences when comparing the two conditions.

The drawback of the design is the potential of "carryover effects", i.e. experience from one condition can affect outcome or performance in the other condition, creating a confounding extraneous variable that varies with the independent variable. Such effects are: practice, positive carryover effect to the latter condition; and fatigue, negative carryover effect to the latter condition.

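### Section 10.1's two-tailed, margin-free test does not implement the ten one-sided non-inferiority tests in Table 4 and conflicts with the one-tailed calculation in section 10.2

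*Combined protocol and SAP*

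**What the plan says.** Section 10.1 names the tests once, for everything: "the hypotheses will be tested using a two-tailed, paired" t-test. The fallback is equally general: "Non-normal data will be tested using the Wilcoxon signed-rank test". Neither sentence mentions a margin, a shift, a direction or a confidence bound, and non-inferiority rows are not excepted. The section then adds: "Acceptance criteria for the data, as applicable, is defined in Table 4".

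Section 7 defines μ1 as the comparator mean, μ2 as the investigational-device mean at two weeks, and |M_NI|, which "is the margin of non – inferiority". In Table 4, nine rows carry ten non-inferiority tests. Row D, for example, says that perceived safety in hill descent "is no worse than with previous prosthesis". Each of the ten has H0: μ1 ≥ μ2 + |M_NI|, H1: μ1 < μ2 + |M_NI| and p<0.05. The margins are 1 (C, D, E, H, I, K), 10T and 3 (G, for PLUS-M and PMQ), 2.5 (L) and 5.5 (N). Table 4's test-method column lists instruments and questions, not statistical tests.

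Section 10.2 sizes the trial with a one-tailed signed-rank test at alpha 0.05. It refers to Table 4 for the pass/fail criteria.

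**The concern.** The only place that names a test gives one that does not match the hypotheses it is meant to test. A two-tailed paired test, in its ordinary meaning, asks whether the mean difference is zero. Table 4 asks whether the device is worse by less than a margin. The text leaves three analyses open:

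1. A two-tailed test of zero difference.
2. A two-tailed test of the difference shifted by the margin.
3. A one-sided test of the shifted difference at 0.05.

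The first does not test Table 4's H0. The second is a valid non-inferiority test only if the direction is also required, and it then runs at one-sided 0.025. The third matches Table 4 and the sidedness of section 10.2, but departs from the word two-tailed in section 10.1.

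The claims of no worse safety on hills and stairs, stance stability, standing comfort, sit-to-stand support, obstacle negotiation, gait functions, mobility and set-up all rest on this choice. The study is unblinded (section 9), so the choice should not be left until the data are in hand.

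**Working it through.** **1. The plan's own figure (section 10.2).** Inputs: dz = 0.7084529, alpha 0.05, one tail, n = 15, A.R.E. method.
- Effective n = 15 × 3/π = 14.324, so df = 13.324.
- Noncentrality = 0.7084529 × √14.324 = 2.6813.
- Critical t (one-tailed) = 1.7676, giving power 0.8150. This reproduces the stated 0.8150214.

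With section 10.1's two tails, the critical t is 2.1550 and power is 0.700. For the paired t-test (df 14, noncentrality 0.7084529 × √15 = 2.7438), two-tailed power is 0.723. Two-tailed power of at least 80% needs 19 completers (signed-rank) or 18 (t-test).

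**2. Direction of Table 4.** H1: μ1 < μ2 + |M_NI| is the same as μ2 − μ1 > −|M_NI|. Section 8.1 says that higher PMQ scores mean higher ability, so this is the correct direction. The 1-10 ratings in D, E, H and I are taken as higher being better, as their own H0 implies.

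**3. Operating characteristics for rows D, E, H and I.** Margin 1, n = 15, df = 14. The documents give no SD of paired differences for these items, so a range of 1 to 2.5 points is assumed. Let Δ be the true difference, device minus comparator. Noncentrality is Δ√15/SD for the zero-difference test and (Δ + 1)√15/SD for the shifted test. Critical t is 2.145 (two-tailed 0.05, or one-sided 0.025) and 1.761 (one-sided 0.05).

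| Probability of p<0.05 | SD 1 | SD 1.5 | SD 2 | SD 2.5 |
|---|---|---|---|---|
| Zero difference, two-tailed, device 1 point worse | 95% | 67% | 44% | 30% |
| Zero difference, two-tailed, devices equal | 5% | 5% | 5% | 5% |
| Shifted, two-tailed p alone, device 2 points worse | 95% | 67% | 44% | 30% |
| Shifted, one-sided 0.05, devices equal | 98% | 79% | 58% | 43% |
| Shifted, one-sided 0.025, devices equal | 95% | 67% | 44% | 30% |
| Shifted, one-sided 0.05, device 1 point worse | 5% | 5% | 5% | 5% |

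The 95/67/44/30 pattern recurs because in each of those rows the truth lies one point from the tested value and the critical t is 2.145. In the first and third rows, the significant results point to a worse device.

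**4. Three worked results (n = 15).**
- Observed mean −1.5, SD 1.5: SE = 1.5/√15 = 0.387. Zero-difference t = −3.87, two-tailed p = 0.0017. Shifted t = (−1.5 + 1)/0.387 = −1.29, one-sided p = 0.89. The 90% interval is −2.18 to −0.82, so non-inferiority is not shown.
- Observed mean −2, SD 1.5: shifted t = −2.58, two-tailed p = 0.022, one-sided p = 0.99. Judged on the two-tailed p alone, this would count as a pass.
- Observed mean −0.3, SD 1: zero-difference p = 0.26. Shifted t = 2.71, one-sided p = 0.008, with 90% interval −0.75 to 0.15. Non-inferiority is shown, yet the zero-difference test misses it.

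**The case against.** The strongest reply is that section 10.1 should be read with Table 4. Sections 10.1 and 10.2 both send the reader there for the criteria, and Table 4 gives every non-inferiority row a numeric margin, a directional H0 and H1, and p<0.05. If p is the p-value against that row's own H0, the criterion is a valid non-inferiority test and a device worse by the margin or more passes only at the nominal error rate. No non-inferiority row states a zero-difference null, and a result in the wrong direction does not support a directional H1. This stands. A reader might infer that the plan adopts a test of difference for its non-inferiority claims, or that its criteria accept a worse device. The documents do not support either inference.

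It is also true that a two-tailed 0.05 test of the shifted difference, with the direction required, gives the same decision as a two-sided 95% interval whose lower limit must exceed minus the margin. On that reading, the change for the t-test is only clarification.

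The reply does not remove the conflict. Section 10.1 never says how the margin enters either test. Its two tails conflict with Table 4's directional hypotheses and with section 10.2, and the one-sided alpha could be 0.05 or 0.025.

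The illustration has limits. It rests on an assumed SD and fits only rows D, E, H and I. Row K is rated by at most 5 CPOs, row C is a two-item total, and G, L and N have other scales and margins.

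**Conclusion.** The conflict is real and should be resolved before analysis. Section 10.1 assigns a test that does not implement the ten non-inferiority tests in Table 4, and its sidedness disagrees with Table 4 and section 10.2. What follows is an undefined analysis, not a demonstrated use of the wrong one, because Table 4 already holds valid hypotheses.

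The size depends on the reading. A literal zero-difference test reaches p<0.05 in 95% to 30% of trials when the device is one point worse, and in only 5% when the devices are equal. A shifted test judged on the two-tailed p alone reaches it in 95% to 30% when the device is two points worse. Unlike the zero-difference test, it does not lose equal devices beyond the cost of working at 0.025. These figures hold for rows D, E, H and I, with 15 completers, normal paired differences and an assumed SD of 1 to 2.5. For the primary endpoint, the two-tailed rule lowers power from 0.815 to about 0.70, using the plan's own effect size.

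**What to change.** Add to section 10.1 that each non-inferiority row is tested one-sided against its Table 4 H0: non-inferiority is claimed only if the lower confidence limit of the mean paired difference (device minus comparator) lies above minus the row's margin. For non-normal differences, apply the signed-rank test to the difference plus the margin, or compare the lower Hodges-Lehmann limit with minus the margin.

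State one one-sided alpha and align it with section 10.2:
- **One-sided 0.05** (90% interval) agrees with section 10.2 as it stands.
- **One-sided 0.025** (95% interval) is stricter. With equal devices it costs about 12 points of power at SD 1.5 (79% to 67%), and between 3 and 14 points over the SDs shown.

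State the sidedness of the primary test as well. If it stays two-tailed, restate the power in section 10.2 as about 0.70 with 15 completers, or plan for 19 completers (signed-rank) to reach 80%. Otherwise the cost is wording only, with no extra visits or measurements.

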### 10.2 Sample size calculation

Power analysis for the estimated required sample size was conducted using G\*Power. See protocol below:

t tests – Means:	Wilcoxon signed-rank test (matched pairs)
Options:	A.R.E. method
Analysis:	A priori: Compute required sample size
Input:	
Tail(s)	= One
Parent distribution	= Normal
Effect size dz	= 0.7084529
$\alpha$ err prob	= 0.05
Power (1- $\beta$ err prob)	= 0.8
Output:	
Noncentrality parameter $\delta$	= 2.6812808
Critical t	= 1.7676466
Df	= 13.3239449
Total sample size	= 15
Actual power	= 0.8150214

It is therefore expected that **at least 15** subjects are required to complete the protocol with a power of **0.8** and significance at **0.05**. Effect size was estimated for the primary endpoint based on a previous in-house study of the RHEO KNEE, a passive microprocessor controlled prosthetic knee.

Given a drop-out rate of **20%**, up to **18** subjects may be recruited.

For pass/fail criteria, see Table 4 **Endpoints, test methods and hypotheses**.

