## 1 How to Refer to This Document

## 2 Summary

Device(s) being tested:	POWER KNEE MAINSTREAM – Dynamic, a pre-market device comparing to users' current microprocessor-controlled knee (MPK). For simplification the device under evaluation in this Clinical Investigation will be referred to as "investigational device" throughout this document.	
Instruments and equipment:	6MWT, Borg scale, Amputee mobility predictor (AMPro), Plus-M (12 item), PEQ, PMQ, L-test, video, data logging by Össur Logic, in house questionnaire for amputee and CPO.	
Subjects recruited:	Inclusion criteria:	Exclusion criteria:
15-18 amputee subjects	50Kg < body weight < 116Kg	50Kg > body weight > 116Kg
Up to 5 CPO subjects	K3-K4 amputees with unilateral transfemoral amputation or Knee disarticulation	Bilateral amputees
	Allows for 37mm knee center height to dome of pyramid alignment	Users with socket problems
	Currently using a MPK or Power Knee	Users with co-morbidities in the contralateral limb, which affect their functional mobility
	Older than 18 years old	Younger than 18 years old
	No socket issues/changes in the last 6 weeks and no socket changes expected during the duration of the study period.	Users with stump pain
	Comfortable and stable socket fit	Users with cognitive impairment
	Willing and able to participate in the study and follow the protocol	Users not involved in other clinical tests and/or receiving treatment that the testing might affect.
Procedures:	This is a prospective two group cross-over study, within subject comparison. 3 study visits are planned for amputee subjects, with approximately 2-3 weeks between visits, and an optional fourth visit 8-12 weeks after the third visit. During the first visit subjects will be checked for inclusion/exclusion, consented and randomly	

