## 8 Design of the Clinical Investigation

### 8.1 General

The test will be a two group prospective cross-over design, within subject comparison. Amputees are a small proportion of the general population. The population group specified in the inclusion/exclusion criteria is a further subsample of amputees. For practical reasons, i.e. to achieve statistical power, it is therefore more feasible to use within-subject comparison rather than creating study arms to compare. Furthermore, as mobile amputees generally have and use a prosthetic device for their daily activities, within-comparison is feasible comparing to the subject's previous device.

All investigational activities will be conducted at MCOP Silver Spring Prosthetic Clinic ([name]), Medical Center Boston, MA Prosthetic Clinic ([name]) and Motus Research ([name]).

As stated above the primary endpoint is the perceived exertion during walking measured by the Borg scale before and after 6MWT, see table 4, and the secondary endpoints are focused on the general mobility performance and efficacy of the investigational device, as well as performance of gait functions and ease of set up for average to highly active transfemoral/knee disarticulation amputees and CPOs. See previous chapter on objectives and hypothesis and Table 4 for rationale.

Drop-outs and withdrawals may be replaced if deemed necessary to fulfil the methodological standards of the study.

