**15-18** subjects are to be enrolled and therefore **15-18** investigational devices will be used, as the devices are intended to be used by a single patient; one for each subject.

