The LPI can withdraw the participant from the trial at any time. The reasons shall be documented. There are no pre-specified criteria for discontinuation of participants from the trial. The discontinuation of participants in the trial will not result in replacement with new participants. If withdrawal is due to problems related to the investigational device the participant will be asked for permission to follow the status/condition outside the clinical investigation. The follow-up will be individualized.

Subjects will be enrolled at the clinic, the investigational site that they were contacted from.

The total time period required to implement the clinical investigation is expected to be 15-20 weeks. Each individual subject is expected to participate in the clinical investigation for 4-15 weeks. The estimated time needed to include this number (enrolment period) is up to 6 weeks.

At least 15 subjects are required to finish the protocol (3 visits) for statistical data analysis, as specified in chapter 10.2 Sample size calculation.

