### 10.3 Additional statistical matters

There is no provision for interim analysis and no criteria for early termination of the clinical investigation on statistical grounds.

Any deviations from the statistical plan provided in this protocol will have to be approved by the sponsor and the reasons for the deviation reported in the clinical investigational report. Dropouts and withdrawn participants will

be included in the data analysis for the procedures that they completed. They will be grouped together and compared to the group that finished the protocol. Any statistical differences of the two groups will be reported. If the participants have not provided any data, they will not be included in the data analysis. No particular information will be excluded from the statistical analysis and tests, as described above.

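### Eighteen recruits do not cover a 20% drop-out from 15 completers, and sections 8.1 and 8.3 contradict each other on whether drop-outs may be replaced

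*Combined protocol and SAP*

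**What the plan says.** The power calculation in section 10.2 ends at "Total sample size = 15", and the text beneath it treats this as a minimum number of completers. The recruitment ceiling follows: "Given a drop-out rate of 20%, up to 18 subjects may be recruited". No inflation formula is shown.

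Section 8.3 sets the same completer requirement: "At least 15 subjects are required to finish the protocol (3 visits) for statistical data analysis". The range is repeated in section 2 ("15-18 amputee subjects") and in section 8.2 ("15-18 subjects are to be enrolled and therefore 15-18 investigational devices will be used").

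Two sections deal with replacement:

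- Section 8.1: "Drop-outs and withdrawals may be replaced if deemed necessary to fulfil the methodological standards of the study".
- Section 8.3: "The discontinuation of participants in the trial will not result in replacement with new participants".

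Section 10.3 adds that dropouts and withdrawn participants will "be included in the data analysis for the procedures that they completed".

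**The concern.** A drop-out rate is normally a fraction of those recruited, so the required number of completers should be divided by the retained fraction. The stated 18 is what results from adding 20% to the 15 completers instead, and it falls one short. Because 18 is worded as a ceiling and repeated as the top of the range elsewhere, the plan has no slack above it.

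Replacement would be the natural way to make up a shortfall, but the plan gives two incompatible rules. Section 8.1 does not say who judges necessity, when, or against what standard. The two rules can lead to different final sample sizes. If the choice between them is made once drop-outs are known, in a study where section 9 says subjects are not blinded, the final sample size rests on an ad hoc decision.

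**Working it through.** **Inputs.** From section 10.2: 15 completers, drop-out 20%, ceiling 18, effect size dz = 0.7084529, one-tailed α = 0.05, target power 0.80, Wilcoxon signed-rank test by the A.R.E. method with a normal parent distribution. From section 8.3: at least 15 must finish three visits.

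**1. Reproduce the 15.** The A.R.E. method uses an effective size N′ = 3n/π, df = N′ − 1 and noncentrality δ = dz × √N′.

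- n = 15: N′ = 14.3239, df = 13.3239, δ = 2.6813, critical t = 1.7676, power = 0.8150. All agree with the printed output.
- n = 14: N′ = 13.3690, df = 12.3690, δ = 2.5904, critical t = 1.7779, power = 0.788.

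So 15 is the smallest n that reaches 0.80 on this basis.

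**2. Reproduce the 18.** 15 × 1.20 = 18.0 exactly. This derivation is inferred, since the plan prints none. Truncating 18.75 would also give 18, and the shortfall is the same either way.

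**3. Number that matches 20% loss.** 15/(1 − 0.20) = 18.75, rounded up to 19.

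**4. What each number delivers at 20% loss.**

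- 18 recruits: 18 × 0.8 = 14.4 expected completers. The largest loss that still leaves 15 is 3/18 = 16.7%.
- 19 recruits: 19 × 0.8 = 15.2 expected completers.

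**5. Chance of 15 completers and average power.** Let X be the number of completers, binomial with retention 0.8. This assumes independent drop-out and no replacement. Average power is the one-tailed A.R.E. power from step 1, weighted by P(X = x).

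| Recruited | Expected completers | P(X ≥ 15) | Average power |
|---|---|---|---|
| 18 | 14.4 | 0.501 | 0.794 |
| 19 | 15.2 | 0.673 | 0.815 |

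With 18 recruits the single most likely count is still 15 (probability 0.230), followed by 14 (0.215).

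**6. Bottom of the stated range.** If only 15 are enrolled, 20% loss leaves 15 × 0.8 = 12 completers, and power at n = 12 is 0.724. The range 15–18 therefore allows for drop-out only towards its upper end.

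**7. The replacement rules side by side.** Section 8.1 permits replacement when judged necessary; section 8.3 excludes it without exception. Suppose a subject is discontinued and replacement is judged necessary: section 8.1 allows a new recruit and section 8.3 forbids one. Nothing in the document gives one section precedence.

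**The case against.** The strongest reply is that the arithmetic slip hardly matters. It is one recruit; average power falls 0.006 short of 0.80, and a study that ends with 14 completers still has 0.788. Section 10.1 makes the paired t-test the analysis when data look normal. On the same dz and one-tailed α its power is 0.806 at n = 14 and averages 0.812 over drop-out with 18 recruits, so on that basis the target is met. This stands, and it is why the point is minor. (Section 10.1 also calls the t-test two-tailed, which is a separate matter.)

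The 20% is also given without a source. If loss were lower, 18 would do better: P(X ≥ 15) is 0.72 at 15% loss and 0.90 at 10% (both rates assumed for illustration). That is true, but the plan chose 20%, and its ceiling should follow from that figure.

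Third, section 10.3 keeps drop-outs' data. A Group 1 subject is tested on the comparator at visit 1 and on the investigational device at visit 2, so one lost after visit 2 may still supply a pair. This helps only in part. Group 2 has no tests at visit 1 and no device data until visit 3. Section 7 defines the comparator mean at 2 weeks, which leaves the use of visit 1 data unclear. The requirement in section 8.3 also counts subjects who finish three visits.

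Finally, replacement under section 8.1 could make up the shortfall. It could, but section 8.3 prohibits it, so this reply depends on the contradiction being settled in one direction.

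**Conclusion.** The concern holds, as a minor point. The ceiling of 18 does not match the 20% drop-out rate attached to it; the matching number is 19. The probability of about one half of reaching 15 completers rests on three assumptions: a true drop-out rate of 20%, independent losses, and no replacement. It counts three-visit completers, not subjects who might still supply a pair. The cost in power is about 0.02 between 18 and 19 recruits (0.794 against 0.815) on the plan's one-tailed Wilcoxon basis.

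The contradiction between sections 8.1 and 8.3 rests on none of these assumptions and is the stronger reason to amend the plan, because it leaves the final sample size undefined once subjects start to leave.

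**What to change.** 1. **Section 10.2, one of two options.**
   - Keep 18 and say that it covers up to three losses (16.7%). This costs one sentence and no subjects, but adds no protection.
   - State 19 as the number matching 20% loss, and change the upper figure in section 2 and the subject and device counts in section 8.2 to agree. This costs edits in three places and at most one more subject and one more device.
2. **Sections 8.1 and 8.3.** Adopt a single replacement rule before enrolment and state it the same way in both. If replacement is allowed, say who decides, what triggers it (for example, fewer than 15 subjects able to finish three visits), and the maximum total enrolled. If it is not allowed, delete the sentence in section 8.1. Ruling replacement out needs only that deletion; allowing it also means replacing the contrary sentence in section 8.3.
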